5.9. Privacy and Confidentiality

5.9.1. **Describe whether the study will use or disclose subjects' Protected Health Information (PHI).**

In order to provide subjects with compensation for enrollment, the study will collect PHI. No PHI will be disclosed to any person outside of the research team.

5.9.2. **Check the PHI to be collected on all subjects for this research protocol.**

Name

All geographic subdivisions smaller than a State, including street address, city, county, precinct, ZIP code, and their equivalent geographical codes, except for the initial three digits of a ZIP code if, according to the current publicly available data from the Bureau of the Census:

- a. The geographic unit formed by combining all ZIP Codes with the same three initial digits contains more than 20,000 people; and
- b. The initial three digits of a ZIP Code for all such geographic units containing 20,000 or fewer people are changed to 000.

All elements of dates (except year) for dates directly related to an individual, including birth date, admission date, discharge date, date of death; and all ages over 89 and all elements of dates (including year) indicative of such age, except that such ages and elements may be aggregated into a single category of age 90 or older.

Telephone numbers

Fax numbers

Electronic mail addresses

Social Security/Medical Record Number

Health plan beneficiary numbers

Account Numbers

Certificate/license numbers

Vehicle identifiers and serial numbers, including license plate numbers

Device identifiers and serial numbers

Web universal resource locators (URLS)

Internet protocol (IP) address numbers

Biometric identifiers, including fingerprints and voiceprints

Full-face photographic images and any comparable images

Any other unique identifying number, characteristic, or code, unless otherwise permitted by the Privacy Rule for re-identification.

HIV (testing or infectious disease) records Sickle cell anemia

Drug Abuse Information

Alcoholism or Alcohol Use

5.10. Information Security

5.10.1. **List the data/information that will be stored (including signed, original informed consent and HIPAA authorization forms, if applicable, case report forms, etc.)**

Stored data and information will include: patient information including name, last 4 of SSN, date of birth, BMI, medical, problem list, signed, original informed consent forms, medication usage, baseline questionnaires capturing participants' sociodemographic information, technology

assessment, and current level of physical activity, any responses from follow-up phone/in-person interviews/surveys.

5.10.2. **Describe the steps that will be taken to secure the data (e.g., training, authorization of access, password protection, encryption, physical controls, Certificates of Confidentiality and separation of identifiers and data).**

All study personnel will complete the required human subjects, HIPAA, and information security and privacy trainings at the VA. Each Veteran who enrolls in this study will be assigned a unique, random patient ID number generated for the purposes of this study. To protect each participant's identity, the link between the Veteran's name, last 4 of SSN, date of birth, and patient ID number will be a password protected file stored on a secure VA server and accessible only to research staff. In all subsequently created analytical files, participants will only be identified by their patient ID number, without inclusion of his/her name, SSN, or date of birth. Subject questionnaires will be either directly inputted into a computer database or written onto paper forms and then transferred to a database at a later time. Interview transcripts will be produced electronically and will be housed on a secure VA server as well. No results will be reported in a personally identifiable manner.

5.10.3. **Indicate how and where data/information will be stored, and specify pertinent security systems.**

The file linking Veterans' personal identifying information, patient database, questionnaire data, and interview transcripts will be password protected and stored on a secure VA server located within the VA firewall. The server is physically located within the FITS computer room of the Philadelphia VAMC and networked within the VA Intranet. Thus, the servers have the same degree of physical and electronic protection afforded other VA computer systems, including antiviral protection and routine back-ups. FITS is responsible for managing the server hardware and software, including its physical and network security and connectivity, backup processes, operating system patches, and application management. Study data will be accessed using password protected computers that are not connected to the Internet and are entirely compliant with Federal Information Security Management Act (FISMA) standards. Paper records will be kept in a locked file cabinet in an electronically secured building. The likelihood of loss of confidentiality is very low given the information security and privacy requirements that are in place.

The study will use the "*Way to Health*" (WTH) platform to provide close monitoring, feedback and reinforcement at a low cost to permit cost-effective flexible, scalable infrastructure. This platform has been used for clinical trials at the CMCVAMC in the past. The platform was built at the University of Pennsylvania and aims to improve health behaviors and consists of a portal with links to variety of peripheral devices (e.g., scales, wearable devices, glucometers) for assessing health behaviors and outcomes; the capacity to communicate back to patients using interactive voice recording; and the ability to automate the delivery of feedback reports. For this study, medication use and step goal data will be collected via the platform.

Once patients have consented to be in the study and have their data managed by WTH, the WTH platform adherence tracking information will be stored according to a unique, random, patient identifier generated for the purposes of the study. To assure that subject, physician and other informant confidentiality is preserved, individual identifiers (such as name and medical record number) are stored in a single password protected system that is accessible only to study research, analysis and IT staff. This system is hosted onsite at the University of Pennsylvania (UPenn) and is protected by a secure identification number (ID). Any datasets and computer files that leave the firewall will be stripped of all identifiers and individuals will be referred to by their study ID. The study ID will also be used on all analytical files.

The University of Pennsylvania Biomedical Informatics Consortium (BMIC) is the hub for the hardware and database infrastructure. The data collected for WTH based studies is stored in MySQL databases on a BMIC-operated blade server environment devoted specifically to WTH. The data center is housed in the Information Systems and Computing at [name]. All data are stored in a single relational database, allowing researchers to correct mistakes. Every SQL transaction, including accessing and changing data is logged for auditing purposes. Data are entered into the database through several different mechanisms. A program specialist will enter subjects' unique, random patient identifier and responses to survey questions through a PHP-based web interface (which is based at the BMIC, as noted above). Data from monitoring devices are uploaded automatically. Datasets are blinded of all personally identifiable information when exported for analysis. The web application automatically removes all identifiers when a member of the research team requests an analytic dataset. The only people with access to identifiable participant information are pre-specified Research Coordinators responsible for contacting participants. Personal information and research data will be stored in separate SQL tables and will be linked by a computer-generated ID number. All data for this project will be stored on the secure/firewalled servers for the BMIC Data Center, in data files that will be protected by multiple password layers. These data servers are maintained in a guarded facility behind several locked doors, with very limited physical access rights. They are also cyber-protected by extensive firewalls and multiple layers of communication encryption. Electronic access rights are carefully controlled by UPenn system managers. We believe this multi-layer system of data security, identical to the system protecting the University of Pennsylvania Health System medical records, greatly minimizes the risk of loss of privacy.

5.10.4. **Will PHI be transmitted or transported outside of CMCVAMC?** ***NOT APPLICABLE***
As noted above, all PHI will be stored on a VA server located behind a VA firewall.

If yes, complete sections 5.10.4.1 through 5.10.4.3, and an Off-site Storage/Transfer of Research Data form. If no, go directly to section 5.11.

5.10.4.1. Does the informed consent document and Authorization for Use & Release of Individually Identifiable Health Information for Veterans Health Administration (VHA) Research form disclose entities/individuals to which/whom PHI will be transported or transmitted? ***Choose an item.***

5.10.4.2. Specify entities/individuals outside CMCVAMC to which/whom data will be disclosed, the justification for such disclosure and the authority, and how they will access it.

5.10.4.3. List the data/information that will be transmitted or transported, and specify how data will be transported or transmitted from one location to another and how it will be protected during transmission or transportation outside of CMCVAMC.

5.11. **Data Management Access Plan**

5.11.1. DMAP form must be included with all initial submissions. The DMAP form can be found on the Research and Development SharePoint site.

5.12. **Communication Plan**

5.12.1. **Include plan for ensuring that the study is conducted according to the IRB-approved protocol.**

All study personnel will meet regularly to ensure that the study is conducted according to the IRB approved protocol. At these meetings, they will discuss unforeseen challenges as they arise and together create a plan for troubleshooting these issues within the confines of the IRB approved protocol.

5.13. **Is this Study Investigating the Use of a Drug or Biological Agent?** **NO** If yes, complete the rest of this section. **If no, go directly to section 6, unless 5.13 applies.**

5.13.1. **Specify if the drug or biological agent is:**

5.13.1.1. **FDA approved:** *Choose an item.*

5.13.1.2. **Used for off-label purposes:** *Choose an item.*

5.13.2. **Include the FDA Investigational New Drug (IND) number for all non-FDA approved and off-label drugs, biological agents or nutritional supplements. If not applicable state, "Not Applicable."**

5.13.3. **Provide all relevant information about the drug, including pre-clinical data.**

5.13.4. **Explain any wash-out periods, rescue medications permitted and any type of medications not permitted while enrolled in the study.**

5.13.5. **Describe blinding and un-blinding procedures.**

5.13.6. **Include the dosage, route of administration, previous use, and the safety and efficacy information on any drug used for research purposes.**

5.13.7. **Describe rationale for the dosage in this study.**

5.13.8. **Justify why the risks are reasonable in relation to anticipated benefits and/or knowledge.**

5.13.9. **Describe where drug preparation will be done.**

5.13.10. **All drugs for CMCVAMC subjects must be dispensed through the VA investigational pharmacy.**

5.13.11. **Describe where the study treatment will be administered.**

5.13.12. **Describe plan for tracking a non-compliant treatment study subject.**

5.13.13. **Describe the process for the storage, security, dispensing and return of an investigational drug.**

5.13.14. Has this protocol has been submitted to the Medical Center's Pharmacy and Therapeutics Committee? *Choose an item.*

5.14. **Is this Study Investigating the Use of a Device** - *NOT APPLICABLE* If yes, complete the rest of this section. **If no, go directly to section 6.**

5.14.1. The Investigational Device Exemption (IDE) number must be submitted for all significant risk devices and if an IDE exists for a non-significant risk device.

5.14.2. **Significant Risk or Non-significant Risk** - If a device is not approved by the FDA, specify whether or not the sponsor has determined this device to be a "significant risk" or "non-significant risk" as defined by the FDA.

5.14.3. **Provide all relevant information about the device.**

5.14.4. **Describe blinding and un-blinding procedures.**

5.14.5. **Specify if device is:**

5.14.5.1. **FDA approved:** *Choose an item.*

5.14.5.2. **Used for off-label purposes:** *Choose an item.*

5.14.6. **Explain if the investigational device will be delivered and/or stored by the Principal Investigator or Pharmacy Service.**

5.14.7. **Describe the process for the storage, security, dispensing and return of an investigational device.**

5.14.8. **For research involving an investigational device, describe the SOP or plan for device control.**

5.14.9. **Address how the device will be stored in such a way that only research staff associated with the protocol will have access to the device.**

5.14.10. **Describe measures that will be put into place to ensure that the device will only be used in subjects of this research protocol.**

Section 6: Resources and Personnel

6.1. **Include where and by whom the research will be conducted.**

The study will be coordinated out of the CMCVAMC . The team includes: [name] (Principal Investigator), [name] (Co-Principal Investigator), [name] (Project Manager) and [name] (Statistician).

6.2. **Provide a brief description of each individual's role in the study. Indicate who will have access to protected health information and who will be involved in recruiting subjects; obtaining informed consent; administering survey/interview procedures; and performing data analysis.**
The team includes: [name] (Principal Investigator), [name] (Co-Principal Investigator), [name] (Project Manager) and [name] (Statistician). These team members will only have access to PHI and will be working collectively to recruit subjects, obtain consents and administer surveys. [name] will perform data analysis.

6.3. **If applicable, provide information on any services that will be performed by contractors, including what is being contracted out and with whom.**
Not applicable.

6.4. **If applicable, provide information on any Memoranda of Understanding (MOUs) or Data Use Agreements (DUAs) that are being entered into, including with whom and for what reason.**
Not applicable.

Section 7: Genetic Testing

7.1. **Does the project involve genetic testing?** *Not Applicable, SKIP TO SECTION 8*

7.2. **Will specimens be kept for future, unspecified use?** *Choose an item.*

7.3. **Will samples be made anonymous to maintain confidentiality?** *Choose an item.* *(If there is a link, it is not anonymous. Coding is not anonymous.)*

7.4. **Will specimens be destroyed after the project-specific use is completed?** *Choose an item.*

7.5. **Will specimens be sold in the future?** *Choose an item.*

7.6. **Will subjects be paid for their specimens now or in the future?** *Choose an item.*

7.7. **Will subjects be informed of the results of the specimen testing?** *Choose an item.*

7.8. **Are there any implications for family members based on specimen testing results?** *Choose an item.*

7.8.1. **If answer to section 7.8 is yes, they may be subjects.**

7.9. **Will subjects be informed of results obtained from their DNA?** *Choose an item.*

7.10. **Explain if the study is looking for an association between a genetic marker and a specific disease or condition, but at this point it is not clear if the genetic marker has predictive value.**

7.11. **Describe if the study is based on the premise that a link between a genetic marker and a specific disease or condition is such that the marker is clinically useful in predicting the development of that specific disease or condition.**

7.12. **Will the subject be notified of the results and the provision for genetic counseling?** *Choose an item.*

Section 8: International Research

8.1. **Does this study involve international research?** *NOT APPLICABLE* If no, go directly to section 9.

Section 9: Statistical Analysis

- 9.1. **Include statistical power calculations and the assumptions made in making these calculations.**
Being a pilot study, the enrollment goal of 40 patients was chosen based on feasibility given the time-frame as opposed to formal power analysis.
- 9.2. **Define plans for data and statistical analysis, including key elements of the statistical plan, stopping rules and endpoints.**
Data from the clinical trial will be analyzed using statistical software in SAS or R. Changes in pain severity, function, opioid analgesic use and physical activity over time will be compared between subjects assigned to each study arm. Regression analyses will be completed to assess if baseline patient characteristics impact the efficacy of the TEC-linked behavioral incentive intervention on key study outcomes.
- 9.3. **Provide sample size determination and analysis (include anticipated rate of screen failures, study discontinuations, lost to follow-up, etc.)**
See above.
- 9.4. **Describe how, where and by whom the data will be analyzed.**
The data will be analyzed by [name] and [name] with the help of a contracted statistician ([name]).

Section 10: References

1. Nahin RL. Estimates of pain prevalence and severity in adults: United States, 2012. *J Pain*. 2015;16(8):769–780.

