Procedures. Eligible patients will be offered participation in this pilot study. The enrollment goal of 40 patients was chosen based on feasibility given the time-frame. Following informed consent, participants will be randomly assigned to one of the two study arms. All participants will be provided individual activity regimens, and be offered physical therapy, yoga, or tai-chi classes at the CMCVAMC. The activity goal will be participation in their activity regimen or classes at least twice per week, a frequency used in other studies promoting activity for chronic pain. Participants will self-report their activity, pain severity, functionality, and opioid use monthly via questionnaire and pill counts. Additionally, all participants will be provided an activity tracker to measure steps taken and instructed on use and data upload procedures. Upon the completion of their 12-week participation, participants are asked to complete an in-person exit survey answering questions about their experience in the study, the use of the FitBit activity watches, as well as the use of the FitBit application.

Those receiving the TEC-linked intervention will be familiarized with the text messaging process and the measures that will be administered via this technology. TEC will consist of a daily personalized text message from a dedicated research assistant reminding the patient to engage in their prescribed physical activity for the day. A second text message at the end of the day will direct the patient to return activity participation, pain severity, functionality, and opioid use data, and upload activity tracker data to the Way to Health (WTH) platform. The behavioral incentive provides the opportunity for subjects who meet their weekly activity goals to enter a lottery to receive either a small (\$30) or large (\$100) financial incentive. The lottery is structured such that subjects have an 18% chance/week of winning the small prize, and a 1% chance of winning the large prize. For those not meeting goals, they will be informed what they would have won had they met their goal. This design has been used in similar studies, with evidence showing the desire to avoid regret can be motivating.

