Measures. The validated NIH PROMIS measures will be utilized to measure key study outcomes. Opioid use will be collected via the WTH Medication Adherence measure and monthly pill counts, and physical activity collected by self-report and a wearable activity tracker. In addition to collection of baseline demographic data and study experience data, study measures will be administered at the specified time points to evaluate the efficacy of the TEC intervention:

Measure	Tool	TEC administration
---------	------	--------------------

Pain severity	PROMIS Pain Intensity	Daily via text
Function	PROMIS Pain Interference	Daily via text
Opioid use	Medication Adherence tool, Pill counts	Daily Beginning and End
Physical activity	Stanford exercise questionnaire Wearable activity tracker	Weekly via text Weekly download
Anxiety, depression, general well-being	PROMIS-29 profile PHQ9	Monthly Monthly

Investigative team: Our interdisciplinary team includes a wealth of experience, including nationally known researchers in chronic pain ([name]), as well as the medical director of the new Pain-PACT ([name]). In addition, our team boasts expertise in connected health interventions using behavioral incentives ([name]).

Study Timeline. Study start-up procedures, including IRB approval and development of text messaging intervention, will take place during the first 3 months of the funding period. Subject recruitment will begin in month 4 and end in month 7, with data collection completed by study month 10. Months 11 and 12 will be devoted to data analysis and dissemination activities.

5.1.2. **What research methods will be used in the project? *Check all that apply.***

 Surveys/Questionnaires	 Interviews	 Audio Taping
 Behavioral Observations	 Chart Reviews	 Video Taping
 Focus Groups	 Randomization	 Double-Blind
 Control Group	 Placebo	 Withhold/Delay Treatment
 Specimen Collection	 Deception	 Telephone Survey

X Other (Describe) Mobility tracking via a wearable device.

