Veterans will be informed of the opportunity to participate in the study by [name] and provided with a copy of a study flyer, and study contact information. The study team will call the veteran 7 days provision of materials. If an individual is interested in the study, they will be asked to review the informed consent and be given the opportunity to ask questions. Once a signed informed consent is returned to the study team, a visit with the veteran will be scheduled to conducted eligibility and baseline surveys. The study team will provide the veteran a wearable device to track step counts and provide instructions to create an account by which they will transmit de-identified step data to the research team and how to access and use the WTH application.

5.2.4. **Will you be using any of the following methods to recruit subjects? (Check all that apply.)**

- Local database for which subjects have NOT given prior permission to be contacted for Research.
- Personal contact with patients over whom you have direct/indirect oversight
- Provider (Clinician) Referrals of potential subjects

5.2.5. Indicate the types of recruitment/advertisement materials that will be used: Check all that apply. Submit copies of recruitment materials, for IRB review.

X Not applicable; none to be used

- Fliers Newspapers Letters Websites Television
- Radio Audio Video Surveys
- Other (Specify, e.g. employee newsletters)

5.2.6. Non-Veteran Subjects will be given a copy of the Notice of Privacy Practices. ***NOT APPLICABLE***

5.3. **Compensation for Participation** - ***YES*** If yes, complete the following.

5.3.1. Summarize any financial compensation that will be offered to subjects.

All participants will receive \$75 to for completing the entire 12-week study. As noted above, they also have the possibility of receiving a financial incentive via a lottery process for meeting activity goals.

5.3.2. Provide the schedule for compensation.

5.3.2.1. Per study visit or session.

N/A

5.3.2.2. Total amount for entire participation.

\$75 if subject completes the entire 12-week study.

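### Section 9.2 compares changes between arms without baseline adjustment; adjusting for a pre-randomisation value would give a modest gain in precision at almost no cost, and steps need a follow-up comparison because no pre-randomisation step value is described

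*Combined protocol and SAP*

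**What the plan says.** **Analysis.** Section 9.2 is the only analysis text. It states: "Changes in pain severity, function, opioid analgesic use and physical activity over time will be compared between subjects assigned to each study arm". No model or covariate is named for that comparison. Baseline data enter once, in regressions meant to "assess if baseline patient characteristics impact the efficacy of the TEC-linked behavioral incentive intervention". That is a question about effect modification, not an adjustment of the arm comparison.

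**Follow-up.** Section 5.1.1 (Procedures) says, for all participants: "Participants will self-report their activity, pain severity, functionality, and opioid use monthly via questionnaire and pill counts".

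**Baseline.** Section 5.1.1 (Measures) opens its list of measures with: "In addition to collection of baseline demographic data and study experience data". It does not say that the outcome measures are taken at baseline. Its table gives the pill-count schedule as "Beginning and End", whereas the text of Procedures and Measures has pill counts monthly. Section 5.2.3 says that after consent "a visit with the veteran will be scheduled to conducted eligibility and baseline surveys", without listing the surveys. Section 5.10.1 includes how active the patient currently is among the items in the baseline questionnaires, but does not name the instrument.

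**Order.** Section 5.1.1 says: "Following informed consent, participants will be randomly assigned to one of the two study arms". The baseline visit also follows consent. Nothing says which comes first.

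**Steps.** Section 5.1.1 says "all participants will be provided an activity tracker to measure steps taken", and 5.2.3 has the device handed over in connection with the baseline visit. No wear period before randomisation is described. Section 5.6.1.1 says activity is stepped up gradually over the first month. Section 4.1 makes tracker-measured mobility part of the primary outcome.

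**The concern.** A reader who takes 9.2 literally would subtract baseline from follow-up and compare the differences. That fixes the coefficient on baseline at 1. Unless baseline and follow-up are very highly correlated, the subtraction adds baseline noise, which a regression on baseline avoids. Section 9.1 sets the size at 40 by feasibility, so wording is a cheaper way to narrow the intervals than more patients.

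Steps raise a separate matter. A change needs a starting value, and none is defined. If the first tracker week were used and fell after randomisation, it would lie within the ramp-up period and, in the intervention arm, within the period of daily prompts. It could already carry part of the treatment effect and would not be a baseline.

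**Working it through.** **Inputs.** From the documents: 40 patients, 20 per arm (5.2.1), with no power calculation (9.1), so there is no planned figure to reproduce. Assumed, because the documents give none: two-sided 5% test, 80% power, effects in SD units, equal SDs at baseline and follow-up, one covariate, and r from 0.3 to 0.8.

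**Formulas** (n per arm, N = 2n, variances in units of SD²):

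- Unadjusted change at one time: V = 2(1 − r), df = N − 2.
- Follow-up adjusted for baseline (ANCOVA): V = (1 − r²)(N − 3)/(N − 4), df = N − 3. With N = 40 the penalty is 37/36.
- Standard error of the arm difference = √(2V/n). The detectable difference comes from the noncentral t distribution.

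**Single follow-up time, n = 20.** Example at r = 0.5: change V = 2 × 0.5 = 1.000; adjusted V = 0.75 × 37/36 = 0.771; ratio 1.30.

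| r | V change | V adjusted | Ratio | Detectable difference (SD), change v adjusted | 95% half-width (SD), change v adjusted |
|---|---|---|---|---|---|
| 0.3 | 1.400 | 0.935 | 1.50 | 1.08 v 0.88 | 0.76 v 0.62 |
| 0.5 | 1.000 | 0.771 | 1.30 | 0.91 v 0.80 | 0.64 v 0.56 |
| 0.7 | 0.600 | 0.524 | 1.14 | 0.70 v 0.66 | 0.50 v 0.46 |
| 0.8 | 0.400 | 0.370 | 1.08 | 0.58 v 0.55 | 0.41 v 0.39 |

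A simulation of 20,000 trials per value gave adjusted/change variance ratios of 0.67, 0.77 and 0.87 at r = 0.3, 0.5 and 0.7, the reciprocals of the ratios above to within simulation error. If 20% are lost (assumed; 16 per arm, penalty 29/28), the detectable differences are 1.21 v 1.00, 1.02 v 0.90 and 0.79 v 0.75 SD at r = 0.3, 0.5 and 0.7.

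**Limits of the gain.**

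- Break-even: 2(1 − r) = (1 − r²) × 37/36 gives r = 72/37 − 1 = 0.946.
- Unequal SDs: if the follow-up SD is k times the baseline SD, the variance ratio change/adjusted is (1 + k² − 2rk) / [k²(1 − r²) × 37/36]. With k = 1.2 it is 1.28, 1.12, 1.01 and 0.98 at r = 0.3, 0.5, 0.7 and 0.8. Before the penalty, the change variance exceeds the adjusted variance by (1 − rk)², which is never negative. Any reversal therefore comes only from the factor 37/36.

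**Mean of the monthly values instead of one time.** Take three follow-ups with common correlation r (assumed). Unadjusted change to the mean has V = 4(1 − r)/3. Adjusted, V = [(1 + 2r)/3 − r²] × 37/36.

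| r | V change to mean | V adjusted mean | Detectable difference (SD), change v adjusted |
|---|---|---|---|
| 0.3 | 0.933 | 0.456 | 0.88 v 0.61 |
| 0.5 | 0.667 | 0.428 | 0.74 v 0.60 |
| 0.7 | 0.400 | 0.319 | 0.58 v 0.51 |

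For the same follow-up summary, adjustment is again the more precise. Across summaries this need not hold: at r = 0.5, unadjusted change to the mean (0.667) beats adjusted single-time follow-up (0.771).

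**Steps.** Compare mean follow-up steps between arms, adjusted for baseline self-reported activity whose correlation with steps is ρ (assumed): V = (1 − ρ²) × 37/36, against 1 unadjusted. The detectable difference is 0.909 SD unadjusted, and 0.922, 0.880 or 0.799 SD at ρ = 0, 0.3 or 0.5. Break-even is ρ = √(1/37) = 0.16. At ρ = 0 the expected variance cost is 37/36 − 1 = 2.8%. The realised cost varies with chance imbalance and equals t²/38, where t is the two-sample statistic for the covariate. It exceeds 2.8% in about 31% of randomisations and has a 95th percentile of about 11% (2.024²/38 = 0.108).

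**The case against.** **The comparison is with the weakest reading of 9.2.** This stands. A reader might infer that the plan gives up the gap between 1.08 and 0.88 SD. It does not commit to that. The text speaks of change over time, monthly values exist in both arms, and an adjusted model would satisfy the same sentence. The figures show the gap between two permitted analyses.

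**Week 12 is not the obvious target.** This stands too. A reader might infer that the plan ought to have named a week-12 contrast. The precision argument does not support that, since averaging the monthly values is more precise. It is a different estimand, and the choice belongs to the sponsor.

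**No baseline is confirmed.** This stands as a condition. No outcome has a same-instrument value that the documents place before randomisation. The activity item in 5.10.1 may not be the Stanford questionnaire, PROMIS pain intensity and interference are at most implied by 5.2.3, and an initial pill count is an inventory, not a use rate. If the instruments differ, the change-versus-adjusted table does not apply to that outcome.

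**Steps can be compared without a baseline.** This stands in part. A reader might infer that the sponsor must choose a step reference after seeing the data. Section 9.2 does not require this: it refers to physical activity, and weekly downloads allow follow-up to be compared directly. What remains is that 9.2 is worded as change and nothing excludes a post-randomisation week as the reference.

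**It is a pilot.** True, and it limits the severity. It does not remove the case for narrower intervals when the cost is wording.

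**Conclusion.** The point holds as a minor improvement in precision. Section 9.2 does not adjust the arm comparison for baseline. Where a baseline value precedes randomisation, adjustment lowers the expected variance for the same follow-up summary: an unadjusted single-time change has 1.50, 1.30 or 1.14 times the variance at r = 0.3, 0.5 or 0.7. These ratios rest on equal SDs, 20 per arm and assumed correlations. The benefit is negligible at very high r and can turn into a small expected loss when the follow-up SD is well above the baseline SD.

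A reader might go further and call the change-score analysis biased. For outcomes with a pre-randomisation baseline, randomisation makes both analyses valid, and nothing in the documents suggests otherwise. Only for steps would a reference recorded after randomisation be unsound, and the documents do not say that one will be used.

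**What to change.** 1. **Section 9.2, main comparison.** State that each outcome is compared by assigned arm, with the follow-up value or values regressed on arm and that outcome's baseline value, wherever that value precedes randomisation. Name the follow-up summary intended, either week 12 or the mean of the monthly values. Keep the effect-modification regressions as a separate analysis.
2. **Section 5.2.3, confirmation.** State that the baseline surveys precede randomisation, whether the activity item in 5.10.1 is the Stanford questionnaire, and whether PROMIS pain intensity and interference are included.
3. **Opioid use.** Reconcile the pill-count schedule in 5.1.1 (monthly in the Procedures and Measures text; start and finish only in the Measures table) before choosing that model.
4. **Tracker steps.** Compare mean daily steps over follow-up between arms, adjusted for baseline self-reported activity provided it is collected before randomisation, and say that a tracker week recorded after randomisation is not used as baseline.

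**Cost.** Wording in 9.2, 5.2.3 and the 5.1.1 schedule, and one degree of freedom per single-follow-up model. For steps, the expected variance cost is about 2.8% if self-reported activity is unrelated to steps, and more in some randomisations. No visit or device is added. If PROMIS pain intensity and interference are not in the baseline surveys, adding them is a small extra burden and that part is not free.
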